5 TRIAL SETTING

This is a multicentre non-commercial trial held in the UK.

Recruitment will be from outpatient MS and OT clinics (for which MS patients are registered) in 10 NHS sites across the UK. The intervention can be completed remotely via the online platform. Self-report questionnaires will be available in paper- or digital-format.

6 PARTICIPANT ELIGIBILITY CRITERIA

6.1 Inclusion criteria

- Participants capable of giving informed consent
- Age 18 years or above
- Currently in paid employment with an intention to remain in employment for at least 6 months
- Phase 2: A registered healthcare professional or allied health professional who works in direct contact with patients diagnosed with Multiple Sclerosis OR
- Phase 3: An individual with a clinical diagnosis of Multiple Sclerosis and reporting a WI score ≥11/22 (on MS-WIS)

6.2 Exclusion criteria

- Individuals lacking capacity to give informed consent
- Individuals intending to leave paid employment within the next 6 months
- Individuals who will not have access to a device used to access the internet (e.g. laptop or smartphone) for the duration of study participation

7 TRIAL PROCEDURES

7.1 Recruitment

Phase 2: HCPs

The research team or site PI will approach relevant healthcare professionals for recruitment. Registered or allied healthcare professionals (n=50) who are responsible for patients with MS will be approached and invited to participate; this includes MS nurses, Physiotherapists, and Occupational Therapists. Healthcare professionals can also self-refer to the trial from enrolled NHS study sites. Potential participants will be provided a PIS and given time to consider participation (minimum 24 hours). Potential participants will have opportunity to ask any questions about participating in the trial and then asked if they wish be enrolled. Participants will be informed that they can withdraw at any time without needing to give a reason. See Table 2 for Schedule of Procedures.

Phase 3: PwMS

Recruitment will be from outpatient MS clinics, daycase units, or OT clinics (in which MS patients are registered) from 10 NHS sites across the UK. The outpatients department and day-case units will be the same locations which patients routinely attend for their regular clinical visits and will be a familiar environment for the participants. Potential participants will be provided a PIS and given at least 24hours to consider the study. Potential participants will have opportunity to ask any questions about participating in the trial and then asked if they wish be enrolled. Participants will be informed that they can withdraw at any time without needing to give a reason. See Table 3 for Schedule of Procedures.

Healthcare professionals on each site will help to identify PwMS who may be interested in participating in the trial.

This study will aim to recruit from a diverse range of backgrounds including socio-economic background, demographic factors, and employment factors.

7.1.1 Screening

Phase 2: HCPS

Healthcare professionals who wish to take part in the study must have responsibility for patients with Multiple Sclerosis as a part of their regular caseload.

Phase 3: PwMS

The MS Work Instability Scale (MS-WIS) will be used as a screening tool to identify subjects with medium or high levels of work instability (WI). In the baseline population from a longitudinal study of 208 PwMS, 20.2% had high WI, 37.0% had medium WI and 42.8% had low WI³⁸.

Potential participants for phase 2a (PwMS) who wish to be enrolled in the study will be invited to complete the MS-WIS. Respondents who report a score of ≥11 on the MS-WIS will be invited to enter the study.

7.1.2 Payment

The participants will not receive any financial incentives to participate in the study.

7.2 Consent

The Principal Investigator (PI) retains overall responsibility for the conduct of research at their site, this includes the taking of informed consent of participants at their site. They must ensure that any person delegated responsibility to participate in the informed consent process is duly authorised, trained and competent to participate according to the ethically approved protocol, principles of Good Clinical Practice (GCP) and Declaration of Helsinki.

Potential participants must be given a minimum of 24 hours from receiving the PIL to consider the study prior to providing consent. Delegated research team members who conduct consent conversations will ensure that the potential participant has understood each statement of consent presented on the ICF and ensure any questions have been answered satisfactorily. Potential participants will be made aware of their right to withdraw at any time without needing to give a reason.

Potential participants who are unable to attend a face-to-face consent conversation for any reason will have the option to complete a secure digital consent form remotely. For remote consent-taking, the researcher must conduct the consent process via telephone or conferencing platform (e.g. Microsoft Teams) and receive verbal consent in addition to the potential participant completing the digital consent form.

All participants will be given a signed copy of the ICF for their own records. For PwMS, a copy will also be included in their medical records and a letter sent to their GP.

7.3 Baseline data

Phase 2: HCPS

Following an introductory virtual workshop, HCPs who have consented to the study will be invited to complete a baseline questionnaire pack which will collect data on:

- Professional group
- Validated self-report scales for Resilience (CD-RISC-10) and Psychological Flexibility (MFPI; see Table 1).
- Free-text responses for their expectations about the READY programme

Phase 3: PwMS

At baseline, demographic data for consented participants will be collected from medical records to include:

- Date of birth
- Sex
- Confirmed MS diagnosis and subtype
- Year of onset and diagnosis
- DMT status

Participants who have consented to and entered the study will be invited to complete a baseline questionnaire pack. The questionnaire pack will be available to be completed digitally and will collect the following data:

- Gender identity
- Ethnicity
- Employment status
- Employment contract type
- Household income
- Number of sick days taken in last 6 months
- Relapse occurring in last 6 months
- Anchor VAS question on general health rating
- Validated self-report scales for Work Instability (MS-WIS), Resilience (CD-RISC-10), Psychological Flexibility (MFPI), Self-efficacy (USE-MS), Mood (HADS), and Impact of MS (MSIS-29; see Table 1)

Table 1 - Validated scales

Full title (Acronym)	Items	Measure	Citation
Multiple Sclerosis Work Instability Scale (MS- WIS)	22	Work Instability	McFadden E, Horton MC, Gilworth G, McFadden M, Tennant A. (2011), Screening for the risk of job loss in multiple sclerosis: Development of an MS-specific Work Instability Scale (MS-WIS)., Multiple Sclerosis Journal, 18, 862-870
Connor-Davidson Resilience Scale (CD- RISC-10)	10	Resilience (Attribute, some process)	Connor, K. M., & Davidson, J. R. (2003). Development of a new resilience scale: the Connor-Davidson Resilience Scale (CD-RISC). Depression and anxiety, 18(2), 76–82. https://doi.org/10.1002/da.10113
Multi-dimensional Psychological Flexibility Inventory (MFPI)	60	Psychological Flexibility	Rolffs, J. L., Rogge, R. D., & Wilson, K. G. (2016). Disentangling Components of Flexibility via the Hexaflex Model Development and Validation of the Multidimensional Psychological Flexibility Inventory (MPFI). Assessment, 25(4), 458–482. https://doi.org/10.1177/1073191116645905 .
Unidimensional Self- efficacy scale for MS (USE-MS)	12	Self-efficacy	Young, C. A., Mills, R. J., Woolmore, J., Hawkins, C. P., & Tennant, A. (2012). The unidimensional self-efficacy scale for MS (USE-MS): developing a patient based and patient reported outcome. Multiple sclerosis (Houndmills, Basingstoke, England) , 18(9), 1326–1333. https://doi.org/10.1177/1352458512436592
Hospital Anxiety and Depression Scale (HADS)	14	Mood (Anxiety and Depression)	Zigmond AS, Snaith RP. The hospital anxiety and depression scale. Acta Psychiatr Scand. 1983 Jun;67(6):361-70. doi: 10.1111/j.1600-0447.1983.tb09716.x. PMID: 6880820.
Multiple Sclerosis Impact Scale (MSIS-29)	29	Psychological and Physical Impact of Multiple Sclerosis	Hobart J, Lamping D, Fitzpatrick R, Riazi A, Thompson A. The Multiple Sclerosis Impact Scale (MSIS-29): a new patient-based outcome measure. Brain. 2001 May;124(Pt 5):962-73. doi: 10.1093/brain/124.5.962. PMID: 11335698.
System Useability Scale (SUS)	10	User satisfaction	Brooke, J. (1996). SUS: a "quick and dirty'usability. Usability evaluation in industry , 189 (3), 189-194.

7.4 Follow up data

Phase 2: HCPS

T1/Week 3: HCPs will be invited to complete the READY programme. The psychologist or CI will conduct an interval support call with HCPs between weeks 2-4 of completing the programme. The support calls will be audio-recorded. Anonymised troubleshooting examples that arise from these support calls will be utilised to develop 'case examples' in a 'Troubleshooting toolkit'. This troubleshooting toolkit will be shared with PwMS who use the programme and a copy given to HCPs to aid support conversations.

T2/Week 8: At week 8 from baseline (proposed completion of READY modules), HCPs will be invited to complete a follow-up digital questionnaire pack which will collect data on:

- Validated self-report scales for Resilience (CD-RISC-10), Psychological Flexibility (MFPI) and User Satisfaction (SUS; see Table 1).

After completing the READY programme and week 8 questionnaire, HCPs will be invited to take part in a digital training workshop delivered by the psychologist and CI.

HCPs will be invited to complete a knowledge test following the workshop which will measure their ACT-based competencies. A digital free-text response questionnaire will also be sent to HCPs following the workshop to assess their experience of the training and any anticipated barriers to supporting others to complete the programme.

T3/Month 6: HCPs will be invited to complete a further follow-up questionnaire at 6 months, which will collect data on:

- Validated self-report scales for Resilience (CD-RISC-10), Psychological Flexibility (MFPI) and User Satisfaction (SUS; see Table 1).

Table 2 - Schedule of procedures (Phase 2: HCPs)

Phase 2: HCPs	T-2 Approach	T-1 Screening (≥24h)	T0 Baseline (Pre- READY)	T1 Week 3 (± 7 days)	T2 Week 8 (Post- READY)	T3 Month 6
PIS given	Х					
Consent		Х				
Baseline Demographics - Date of birth - Sex - Gender identity - Ethnicity			Х			
Employment demographics - Professional group			Х			
Connor-Davidson Resilience Scale (CD-RISC-10)			Х		Х	Х
Multi-dimensional Psychological Flexibility Inventory (MFPI)			Х		×	Х
System Useability Scale (SUS)					Х	Х
Qualitative: Introductory workshop feedback form (Expectations about READY programme)			Х			
Qualitative: Interval support call audio- recording				Х		
Qualitative: Training workshop feedback form					Х	
ACT-based Competencies					Х	
Qualitative: Semi-structured interviews					Х	

Phase 3: PwMS

T1/Week 3: The HCP will conduct an interval support call with HCPs between weeks 2-4 of completing the programme. HCPs will be encouraged to record notes from these support calls to contribute to lightning reports and the overarching process evaluation

T2/Week 8: Participants will be invited to complete follow-up questionnaire packs at week 8 from baseline. The questionnaire packs will be available to be completed digitally and will collect demographic information to include:

- Employment status
- Employment contract type
- Household income
- Number of sick days taken in last 6 months
- Relapse occurring in last 6 months
- Anchor VAS question on general health rating
- Validated self-report scales for Work Instability (MS-WIS), Resilience (CD-RISC-10), Psychological Flexibility (MFPI), Self-efficacy (USE-MS), Mood (HADS), and Impact of MS (MSIS-29) and User Satisfaction (SUS; see Table 1)

T3/Month 6: Participants will be invited to complete a further follow-up questionnaire pack at month 6 from baseline. The questionnaire packs will be available to be completed digitally and will collect demographic information to include:

- Employment status
- Employment contract type
- Household income
- Number of sick days taken in last 6 months
- Relapse occurring in last 6 months
- Anchor VAS question on general health rating
- Validated self-report scales for Work Instability (MS-WIS), Resilience (CD-RISC-10), Psychological Flexibility (MFPI), Self-efficacy (USE-MS), Mood (HADS), and Impact of MS (MSIS-29) and User Satisfaction (SUS; see Table 1)

.

Table 3 - Schedule of procedures (Phase 3: PwMS)

Phase 3: PwMS	T-2	T-1	T0	T1	T2	T3
	Approach	Screening	Baseline	Week 3	Week 8	Month 6
		(≥24h)	(Pre- READY)	(± 7 days)	(Post- READY)	
PIS given	Х					
Consent		Х				
Screening		Х				
Baseline Demographics - Date of birth - Sex - Confirmed MS diagnosis and subtype - Year of MS onset/ diagnosis - Gender identity - Ethnicity			Х			
MS History - MS subtype - Confirmed relapse(s) (last 6 months) - DMT status			X		Х	Х
 Employment demographics Employment status Employment contract type Household income Number of sick days (last 6 months) 			x			
General health VAS			Х		Х	Х
Multiple Sclerosis Work Instability Scale (MS-WIS)		Х	Х			
Connor-Davidson Resilience Scale (CD-RISC-10)			Х		Х	Х
Multi-dimensional Psychological Flexibility Inventory (MFPI)			Х		Х	Х
Unidimensional Self-efficacy scale for MS (USE-MS)			Х		Х	Х
Hospital Anxiety and Depression Scale (HADS)			X		X	Х
Multiple Sclerosis Impact Scale (MSIS-29)			Х		Х	Х
System Useability Scale (SUS)					Х	Х
Qualitative: Interval support contact notes				Х		
Qualitative: Semi-structured interviews					Х	Х

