Enrolment of NHS MS Centres **Refinement of Digital READY** Ethical Approvals & Digital READY is a web-based resilience training programme for Multiple Sclerosis Governance Enrolment of health professionals (HCPs) in MS (n=50) Digital introductory workshop delivered with Psychologist Outcome Measures: Pre-READY questionnaire (Baseline Psychological Flexibility; Qualitative feedback) HCPs complete Digital READY and training (n=50, 5 HCPs per site) 2a. Digital READY participation Week 3 interval support call (delivered by Psychologist) Development of troubleshooting toolkit Outcome Measures: Psychologist notes on troubleshooting, Post-intervention questionnaire pack (Psychological flexibility, User satisfaction) and 6m follow up questionnaire (Psychological flexibility) 2b. READY training workshop (delivered by Psychologist/Project manager) Outcome Measures: Knowledge/competencies test, qualitative feedback questionnaire Sub-set: Semi-structured audio-recorded research interviews post-READY **Enrolment of PwMS** (n=250; 5 per HCP, 25 per site) Screening: Employment status, MS-WIS (Work Instability), Consent to take part Outcome Measures: Pre-READY questionnaire (Baseline Psychological Flexibility, Work Instability, other psychological factors) **PwMS complete Digital READY** Digital READY participation Week 3 interval support call (delivered by HCP) Outcome Measures: HCP notes on troubleshooting, Post-intervention and 6m follow up questionnaire packs (Psychological flexibility, Work Instability, User satisfaction, other psychological factors) Sub-set: Semi-structured audio-recorded research interviews post-intervention and 6m Analysis and write up Primary outcomes: PWMS MS-WIS at 6m, PWMS Psychological flexibility at 6m, HCP Competency/Knowledge test

Secondary outcomes: HCP Psychological flexibility at 6M

Process evaluation: Qualitative interviews, notes and questionnaire responses

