3 OBJECTIVES AND OUTCOME MEASURES/ENDPOINTS

3.1 Aim/s and Objectives

A digital resilience-training programme called 'READY for MS' has been co-developed in the UK and piloted with PwMS who report work instability. It is important to assess that the digital UK READY for MS programme can be delivered and received as intended; this is known as "Intervention fidelity". Specifically, this study aims to monitor fidelity to function, i.e. measuring the core functions of the READY for MS programme, through psychological self-report measures. This is important for checking (validating) the use of READY for MS in a "real world" setting. To do this, we will train MS healthcare professionals to support the delivery of READY for MS and then check whether it has been delivered and received as intended. We will also check that READY leads to the intended long-term outcomes for PwMS who receive it.

Aim: To assess NHS implementation of an online type of Acceptance and Commitment Therapy (ACT) codeveloped with PwMS 'REsilience and Activities for every DaY for MS' (READY) resource to support resilience at work for PwMS.

This will be delivered through five objectives:

- 1. The feasibility and effectiveness of training MS health practitioners in several NHS centres to support delivery of the digital READY programme to PwMS following an immersive training programme.
- 2. The effectiveness of delivering the READY programme in the NHS for PwMS when supported by trained MS practitioners and the long-term outcomes
- 3. Which/how contexts influence how MS practitioners support/engage with PwMS completing the READY programme?
- 4. Which/how contexts influence how PwMS engage with the READY programme and the long-term outcomes
- 5. To what extent intervention fidelity mediates these long-term outcomes

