3.2 Primary endpoint/outcome

The primary quantitative outcome measures for this study will be work instability, as measured by the MS Work Instability scale, resilience, psychological flexibility, and self-efficacy. We want to check that the digital READY programme will continue to work as

intended when supported by trained healthcare professionals, therefore we would expect to see a psychological benefit for PwMS being supported to use the READY programme in an NHS setting.

We expect that this ACT-based programme should lead to increased resilience, psychological flexibility, and self-efficacy. We theorise that increasing these psychological factors should lead to a reduction in work instability. This should mean we see a significant reduction in work instability in participants who complete the digital READY for MS programme.

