8.2 Statistical analysis plan

This is a hybrid trial assessing implementation and effectiveness of the digital READY programme in NHS settings.

In terms of effectiveness, this study seeks to understand who might benefit from the digital READY intervention and in what contexts. Participant outcomes (e.g. Work Instability, Psychological flexibility, Self-efficacy) will be measured at multiple time-points (baseline, week 8 and month 6). While the first step will be to assess for any change to outcome variables over time using repeated measures ANOVA, this provides only an overview of interventional impact and assumes homogenous change within the study group⁴². Latent Growth Curve Modelling (LGCM) can be useful to identify patterns within subgroups of a population to understand who benefits from an intervention and why⁴³. Latent Growth Curve Modelling (LGCM) will be used to determine trajectories over time. Changes from baseline to week 8 and baseline to month 6 will be assessed. Logistic regression models will be utilised to understand potential predictors of these trajectories. Specifically, the relationship between psychological flexibility, resilience, and work instability, how these change for participants from baseline to post-intervention and longer term, and if changes in these variables seem to be linked. If there is evidence of a relationship between work instability and resilience or psychological flexibility over time, such that increases in resilience or psychological flexibility relate to decreases in work instability, this would suggest that the READY programme could be effective in reducing work instability.

Lightning reports will be produced using rapid qualitative synthesis following a pre-defined framework³⁹. These lightning reports will enable iterative assessments of implementation that will inform the final qualitative assessments.

The process evaluation will help to identify contextual factors that may influence core processes of the intervention through qualitative inquiry.

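### The HCP knowledge test, primary only in the flow chart, is taken once after training, so it can show the level reached but not whether training raised it

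*Protocol*

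**What the plan says.** **Status.** The trial flow chart lists "Primary outcomes: PWMS MS-WIS at 6m, PWMS Psychological flexibility at 6m, HCP Competency/Knowledge test". Section 3.2 gives a different set: "The primary quantitative outcome measures for this study will be work instability, as measured by the MS Work Instability scale, resilience, psychological flexibility, and self-efficacy". The outcome table in the trial summary has the same four constructs as section 3.2 in its primary column, and the HCP test appears in neither its primary nor its secondary column.

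**Objective.** Objective 1 in section 3.1 is "The feasibility and effectiveness of training MS health practitioners in several NHS centres to support delivery of the digital READY programme to PwMS".

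**Timing.** Section 7.4 states: "HCPs will be invited to complete a knowledge test following the workshop which will measure their ACT-based competencies". The row for ACT-based competencies in Table 2 has a single mark, at T2 (week 8). The HCP baseline pack in section 7.3 holds professional group, CD-RISC-10, MPFI and free text, and the month 6 pack holds CD-RISC-10, MPFI and SUS. Neither includes the test. The protocol describes no HCP group without training and states no pass mark.

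**Analysis.** Section 8.2 begins from "Participant outcomes (e.g. Work Instability, Psychological flexibility, Self-efficacy) will be measured at multiple time-points" and assesses change over time by repeated measures ANOVA and growth curve models.

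**The concern.** Asking whether training is effective usually means asking whether people know or can do more after it than before. A single score after training mixes what the HCPs already knew with what they gained. Prior knowledge may well vary here, since section 7.1 recruits nurses, physiotherapists and occupational therapists and allows self-referral.

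The schedule is also uneven. HCP psychological flexibility, which the flow chart calls secondary, is measured at T0, T2 and T3, while the HCP outcome that the flow chart calls primary has no baseline. A high score at T2 could be reported as evidence that training worked when the data fit a large gain and no gain equally well. A missing baseline differs from a missing analysis detail: a statistical analysis plan can choose a method, but it cannot supply a measurement that was never taken.

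**Working it through.** **1. The protocol's own figures.** Section 8.1 sizes the group of people with MS (PwMS): 200 / (1 − 0.20) = 250, which matches the stated target. The HCP number is 10 sites × 5 = 50, which also matches. No power, effect size, SD or pass mark is stated for the HCP test, so there is no HCP calculation to reproduce.

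**2. What one post-training score identifies.** For each HCP, score at T2 = level before training + change since then. Only the left side is observed. With no T0 value and no comparator, the mean change cannot be identified at any sample size.

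**3. Illustration (assumed result).** Suppose 40 of 50 HCPs reach some mark at T2.
- Share reaching it: 40/50 = 80%, exact 95% CI 66% to 90%. The level is reasonably well estimated.
- Change in that share = 80% − share before training. The earlier share could lie anywhere from 0% to 100%, so the change could lie anywhere from +80 to −20 percentage points. If training is assumed to do no harm, the range is 0 to +80.

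**4. What a T0 test would add.** Assumptions: two-sided 5%, 80% power, paired t-test. Normal approximation: detectable change = (1.960 + 0.842) / √n, in SDs of the paired differences.

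| Pairs | Normal approximation | Noncentral t |
|---|---|---|
| 50 | 2.802 / 7.071 = 0.396 | 0.404 |
| 40 | 2.802 / 6.325 = 0.443 | 0.454 |

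The 40 is 50 × (1 − 0.20), borrowing the attrition that section 8.1 assumes for PwMS. These figures cannot be turned into test marks because the SD of the differences is unknown. They also treat HCPs as independent, although they come five to a site.

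**5. What the single test could still support.** Suppose a pass mark is set in advance, with a 70% pass rate taken as inadequate and 90% as the target (both assumed). Exact binomial results, one-sided:
- n = 50, success at 42 or more passes: alpha 0.018, power 0.94.
- n = 40, success at 34 or more passes: alpha 0.024, power 0.90.

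Attainment of a standard is therefore testable with the present schedule; improvement is not.

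**6. Status, side by side.** Flow chart: primary. Section 3.2: absent. Trial summary: absent from both outcome columns. These cannot all be the intended hierarchy.

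**The case against.** A reader might infer that Objective 1 cannot be answered at all and that nothing in an analysis plan could help. The protocol does not support that reading, for three reasons.

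- Objective 1 joins feasibility to effectiveness, and feasibility needs no baseline test.
- Effectiveness of training people to support delivery can reasonably mean that they are competent afterwards. That fits the protocol's emphasis on fidelity, and step 5 shows that one test against a fixed standard is workable. The pass mark may sit in an analysis plan or in the separately held appendices, so its absence from the protocol is no fault in itself. The same goes for the absence of an HCP analysis from section 8.2.
- Other HCP data bear on the objective: repeated MPFI and CD-RISC-10, SUS, recorded support calls, workshop feedback, and interviews on how the core concepts were understood.

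All of this stands, and it narrows the point. What remains is that none of these sources measures a gain in ACT knowledge. MPFI and CD-RISC-10 measure the HCP's own flexibility and resilience, and a pass mark shows attainment without showing that training produced it.

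It is also fair to say that a T0 test is imperfect. The T0 pack follows the introductory session, an uncontrolled change includes any practice effect, and the change covers READY and workshop together. Separating the workshop would need a further test between the two. The addition gives an estimate of change, not a clean causal effect.

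**Conclusion.** The point holds in a limited form. As scheduled, the test can estimate the level HCPs reach but not whether training improved it, and no analysis can recover a baseline that was not collected. This restricts the effectiveness half of Objective 1 and leaves feasibility and the qualitative evidence intact. Separately, the protocol contradicts itself on whether the test is primary, and that needs reconciling whatever is decided about T0.

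The conclusion about identification needs no numerical assumption. The detectable changes of 0.40 SD (50 pairs) and 0.45 SD (40 pairs) rest on assumed 80% power, two-sided 5% and borrowed attrition. The 40-of-50 result and the 70% and 90% pass rates are illustrations only. This is an inexpensive improvement well worth making, not a flaw that undermines the trial.

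**What to change.** 1. Add the same knowledge test to the HCP baseline pack (section 7.3, and Table 2 at T0), to be completed before READY begins.
2. State that the HCP outcome is the paired T0-to-T2 change with a 95% CI, described as an uncontrolled change over READY and workshop combined.
3. For HCPs already past T0, or if no T0 test is added, fix a competency standard before the scores are seen and limit the claim to attaining it.
4. Give the test one status in the trial summary, the flow chart and section 3.2.

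The cost is one extra form for 50 HCPs at a contact that already exists, plus a possible practice effect from seeing the test twice, which should be acknowledged when the change is reported. Items 3 and 4 need only text changes.

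### Table 3 schedules no MS-WIS or employment items after baseline, contradicting the text of section 7.4, the flow chart and, for MS-WIS, sections 4 and 8.2

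*Protocol*

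**What the plan says.** Table 3 in section 7.4 of the protocol is the schedule of procedures for people with MS. It has six columns: approach (T-2), screening (T-1), baseline (T0), week 3 (T1), week 8 (T2) and month 6 (T3). The row "Multiple Sclerosis Work Instability Scale (MS-WIS") carries marks at T-1 and T0 and nothing after. The employment row covers employment status, contract type, household income and "Number of sick days (last 6 months"), and is marked at T0 alone.

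The text of section 7.4 just above the table says otherwise. Its lists for week 8 and for month 6 both contain the four employment items and this line: "Validated self-report scales for Work Instability (MS-WIS), Resilience (CD-RISC-10), Psychological Flexibility (MFPI), Self-efficacy (USE-MS), Mood (HADS), and Impact of MS (MSIS-29) and User Satisfaction". On the later visit it states: "Participants will be invited to complete a further follow-up questionnaire pack at month 6 from baseline".

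The rest of the protocol agrees with that text. Section 3.2 gives the primary quantitative outcomes as "work instability, as measured by the MS Work Instability scale, resilience, psychological flexibility, and self-efficacy". The flow chart fixes the time point: "Primary outcomes: PWMS MS-WIS at 6m, PWMS Psychological flexibility at 6m, HCP Competency/Knowledge test". Section 4 (Phase 3) says that the pack completed at the end of the programme measures work instability and is repeated at 6 months. Section 8.2 names work instability among the outcomes measured at baseline, week 8 and month 6.

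**The concern.** The table and the text cannot both be followed. Section 7.1 sends the reader to Table 3 as the schedule of procedures for this phase. Section 9.1 makes site teams responsible for collecting data and for finding and chasing missing items. A team checking completeness against Table 3 would have no reason to query an absent MS-WIS at week 8 or month 6, because the table shows none as due.

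A participant's own rating of work instability at week 8 or month 6 cannot be taken later. Both MS-WIS assessments in the table come before the programme starts. Where only those exist, neither the repeated measures ANOVA nor the growth curve model of section 8.2 can estimate change in work instability. The question on which section 8.2 rests its conclusion, whether rising resilience or psychological flexibility goes with falling work instability, could not be answered for those participants either.

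**Working it through.** **1. Side-by-side reading.** The table below sets the Table 3 marks against the packs itemised in the section 7.4 text.

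| Item | Table 3 marks | Section 7.4 text, week 8 and month 6 | Follow-up visits marked in Table 3 |
|---|---|---|---|
| MS-WIS (primary) | T-1, T0 | listed at both | 0 of 2 |
| CD-RISC-10 (primary) | T0, T2, T3 | listed at both | 2 of 2 |
| Psychological flexibility scale (primary) | T0, T2, T3 | listed at both | 2 of 2 |
| USE-MS (primary) | T0, T2, T3 | listed at both | 2 of 2 |
| HADS, MSIS-29, general health VAS | T0, T2, T3 | listed at both | 2 of 2 |
| Employment items | T0 | listed at both | 0 of 2 |

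Only the MS-WIS and employment rows depart from the text in this comparison.

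**2. Which side is the outlier.** Four places put MS-WIS or work instability at follow-up: the flow chart, section 4, the section 7.4 text and section 8.2. Only Table 3 leaves it out. For the employment items, the section 7.4 text lists them at both visits, and section 9.1 says the questionnaires at all three time points include work information.

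**3. Could marks have been lost in reading the PDF?** The MS-WIS row keeps all six columns, with its two marks in the right places. The scale rows next to it keep their T2 and T3 marks, and so does the multi-line MS history row just above the employment row. Loss in these two rows alone is unlikely. The employment row reads less cleanly than the MS-WIS row, so both should be confirmed on the source PDF page.

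**4. The plan's own number.** Section 8.1 sets a minimum of 200 cases and assumes 20% attrition: 200 / (1 − 0.20) = 250, which reproduces the target. The site plan agrees: 10 sites × 25 = 250. No sample size changes as a result of this point.

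**5. What the conflict could cost.** Assume that the 20% attrition applies to month 6 and is even across sites.
- Table matches the text: 250 × 0.80 = 200 expected cases with follow-up MS-WIS and three analysis time points (T0, T2, T3).
- One site follows the table as printed: 9 × 25 × 0.80 = 180.
- Each further site that does so removes another 25 × 0.80 = 20.
- Everyone follows the table: 0 cases with follow-up MS-WIS. This is the outer limit, not an estimate.

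Because 200 is exactly the stated minimum, a single site working from the table is enough to fall below it for MS-WIS.

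**The case against.** The strongest reply is that the intent is not in doubt. The section 7.4 text itemises the packs correctly, three other places agree with it, and Table 3 does not itself define what a pack contains. Questionnaires go out mainly through a digital platform, so an omission confined to one site is less likely than it would be on paper. On this view the gap is a clerical slip that a careful reader would resolve correctly.

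Much of that stands. The protocol nowhere says that the packs are built from Table 3, so the harm is conditional. What remains is that the protocol itself names the table as the schedule, allows paper questionnaires (section 5), and leaves missing-data checks to the sites. Clear intent elsewhere does not protect a user who works from the table.

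A reader might infer three stronger things, and the protocol supports none of them.
- That following the table would leave no post-intervention primary data at all. Section 3.2 names four primary outcomes, and Table 3 schedules the other three at both follow-up visits.
- That a planned analysis of job loss would fail. Sections 3.2 to 3.4 list no job-loss or employment-status outcome, and section 8.2 plans no such analysis. The missing employment items would be a loss of data, not of a stated endpoint.
- That faulty packs are already in use. The protocol does not say whether packs are live or how they were built.

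**Conclusion.** Wrong as written. Table 3 omits MS-WIS and the employment items at week 8 and month 6 and so contradicts the text it is meant to summarise. The consequence is confined to participants whose data collection followed the table: for them there would be no post-intervention MS-WIS or employment data, and change in one of the four primary outcomes could not be analysed. The size runs from no loss, if everyone works from the section 7.4 text, through about 20 expected cases for each site that works from the table, to all follow-up MS-WIS in the extreme case.

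The conclusion rests on the table having been read correctly from the PDF, which the intact neighbouring rows make likely. The case counts also rest on the even-attrition assumption stated with them. The contradiction itself depends on no numerical assumption. It deserves correction before the schedule is relied on, because the affected outcome is the one listed first in section 3.2 and a missed self-report cannot be recovered.

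**What to change.** In Table 3, mark the MS-WIS row and the employment row at T2 (week 8) and T3 (month 6), leaving their existing marks in place, so that the table matches the section 7.4 text. Then check that the digital and paper questionnaire packs, and the lists that sites use to identify missing data, agree with the corrected table at both visits.

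The cost is four added marks and one check of the packs and lists, plus whatever amendment notice the sponsor's process requires. No assessment, visit or participant burden is added, because the text already asks for these items, and the target of 250 does not change.
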